Primary Endpoint

The primary objective of the study is to describe the implementation and outcomes of an innovative Smart Clinic model useful for the clinical and pharmacological monitoring of the patient suffering from non-valvular atrial fibrillation treated with new generation oral anticoagulants, in which a community pharmacist, adequately trained, takes on the role of case manager and the patient has the possibility to perform the checks provided in telemedicine and in self-analysis, in the services pharmacy regime, the results of which will be shared in real time with the treating physician and reference specialist of the same.

Secondary Endpoints

The secondary objectives of the study are:

- assessment of adherence to the required controls;
- assessment of the prescriptive appropriateness of the dosages and molecules used;
- assessment of adherence to prescribed therapy;
- assessment of the occurrence of pharmacological problems related to drug-drug interactions;
- assessment of the occurrence of bleeding and / or thrombo-embolic complications;
- evaluation of the acceptance by the General Practitioner and / or the Specialist in Cardiology of the reports made by the pharmacist and the subsequent actions taken;
- assessment of the economic and social impact of this model on the National Health Service and on the patient;
- assessment of the impact on quality perceived by patients in carrying out this innovative monitoring process.

4. Study Procedures

The study, whose duration will be equal to 12 months (September 2021 - August 2022), which does not include any cost for the National Health Service and for the participating patients themselves, is of the following type:

- observational,
- perspective,
- monocentric,
- no profit.

The main phases of the research project are indicated below.

Phase 1: Patient enrollment (September 2021)

In the first phase, lasting a total of one month, patients are enrolled, with the characteristics indicated below, in a number equal to 50.

Phase 2: Review, database validation and definition of Individual Care Plans (September 2021)

In September 2021 we proceed with the validation of the database and with the definition, by the general practitioners involved, of the Individual Care Plans.

Phase 3: Case Management and follow up (September 2021 - August 2022)

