In the remaining months, the Case Manager follows the patients in carrying out the checks required by the guidelines in force, relating to non-valvular atrial fibrillation and concomitant anticoagulant therapy, and by the Individual Care Plan drawn up by the attending physician, in case a personalization of the path is necessary. follow-up dictated by the patient's particular clinical conditions (e.g. impaired renal function). 12-lead ECG (performed with Micotel BT electrocardiograph and reported by the HTN Srl control unit), Holter ECG (performed with Cardioline WALK400H and reported by HTN Srl) self-analysis (hemoglobin, hematocrit and creatine, performed with the Allegro device from Nova Biomedical Italia Srl) will be carried out directly in the pharmacy through the use of the equipment and reporting platforms mentioned above. The control of drug interactions will be performed using the INTERcheck Web platform of the Mario Negri IRCCS Institute for Pharmacological Research.

The follow-up agenda includes the following activities:

Timing	Attività	Note
Enlistement	General health status	
	Pharmacological Therapy	- evaluated at each therapeutic insertion
	12-lead ecg	
	Dynamic ecg sec. Holter	- if not performed within the previous 12 months - if in the FVM ecg > 90 or <60bpm during AF
	Blood chemistry tests	
	Blood pressure and heart rate	
Frequency Monthly	General health status	
	Blood pressure and heart rate	
	12-lead ecg	- if specific symptoms are reported
Quarterly frequency	Single-track ecg	
	Blood chemistry tests	- if clearance ratio creatininemia / 10 = 3
Six-monthly frequency	12-lead ecg	
	Blood chemistry tests	- if patient over 75 and patients with cl cr/10 = 6
Annual frequency	12-lead ecg	
	Dynamic ecg sec. Holter	
	Blood chemistry tests	

After each follow-up meeting, a report including all the measurements made will be sent, through a special telemedicine platform, to a cardiology specialist for an initial analysis. The latter, after a careful evaluation of the documentation received, will forward a feed-back report with any

suggestions for the treating physician and / or the reference specialist, who, based on the knowledge of the patient in question, will define the actions to be taken. .

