For the requested services that cannot be carried out in the pharmacy, the pharmacist proceeds with the execution of the prescription from the General Practitioner, the booking of the examination through the CUP service and the execution of a telephone reminder service that reminds the patient when to carry out the 'examination.

5. Expected duration of the study

The study will run for 12 months, from September 2021 to August 2022.

6. Inclusion and exclusion criteria

ARRUOLABLE patients:

- age> 18 years,
- patients suffering from Non-Valvular Atrial Fibrillation and being treated with new generation oral anticoagulants;
- able to express consent to the study;
- regularly related to the trial site (Farmacia [name] S.r.l.)
- AntiCovid19 vaccination performed

7. Case Report Form (CRF)

Electronic data collection forms are provided (Case Report Form - CRF) necessary for the collection of the patient's clinical information, together with those of an organizational and managerial nature.

The detail of the information to be collected is defined in the data collection forms.

For the purpose of a homogeneous data collection, for each patient belonging to the target population, the compilation of a form is envisaged, the structure of which generally includes the following macro-areas:

- general information about the patient (ID, sex, age, etc.);
- information relating to the family setting (spouse, children, care giver, etc.)
- proximate and distant pathological history
- drug therapy practiced

- vital signs and entry blood tests
- examinations and procedures required for follow up
- results and reports of the checks carried out during the follow-up;
- perceived quality questionnaire.

8. Sample size and statistical analysis

A simple size of 50 patients was defined for the conduct of this study.

The statistical analysis of the collected data will be developed through descriptive analysis.

The economic evaluation will be performed by comparing the costs incurred in the traditional path and the costs resulting from the application of the model under study, calculated by referring to the regional tariff where appropriate.

The assessment of the perceived quality will be carried out through a short anonymous questionnaire administered at the end of the study to all the subjects enrolled.

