All categorical variables measured in this study will be expressed as absolute numbers and percentages. Continuous variables will be expressed as mean and standard deviation or median and interquartile range [IQR], depending on the normal or non-normal distribution of the data.

Differences will be analyzed by chi-square test, unpaired t-test or Mann-Whitney U test, depending on the nature of the variable.

Any difference with a $p < 0.05$ will be considered statistically significant.

9. Results expected from the study

The patient suffering from non-valvular atrial fibrillation and being treated with oral anticoagulants needs his state of health to be in a condition of equilibrium between the risk of bleeding on the one hand and the risk of thrombo-embolism on the other.

For this reason, it is important that this type of patient undergoes constant checks over time to verify that his clinical conditions are always balanced, however, the daily rhythms of life hinder full adherence to the controls.

This study by overcoming this and other critical issues, thanks to the use of the unexpressed potential of the service pharmacy (remote execution of the services provided by the follow-up paths) and of the pharmacist, as case manager, alongside medicine basic and specialized, will allow to improve the current quality of care for the type of patients examined, with a view to safety, efficacy and appropriateness of care on the one hand and sustainability on the other.

10. Ethical considerations

To protect privacy, patients in the group described above will be identified only by means of progressive numerical codes (ID).

The data will be treated with confidentiality and confidentiality and disclosed only in aggregate and anonymous form.

The protection of individuals will be guaranteed as recommended in the Oviedo Convention (Convention for the Protection of Human Rights and the Dignity of the Human Being with regard to the Application of Biology and Medicine: Convention on Human Rights and Biomedicine - April 4, 1997) and in the Declaration of Helsinki relating to ethical principles for medical research and whose aim is to provide advice to doctors and other participants in medical research.

All patients will be required to sign a written Informed Consent, with particular reference to the processing of personal data.

11. Bibliography

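### Section 8 attaches a p<0.05 rule to independent-group tests only and names no contrast; if used for change within the single cohort of 50, it ignores the pairing

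*Combined protocol and SAP*

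**What the plan says.** Section 8 opens with a descriptive plan: "The statistical analysis of the collected data will be developed through descriptive analysis". Its closing paragraphs add a testing rule: "Differences will be analyzed by chi-square test, unpaired t-test or Mann-Whitney U test, depending on the nature of the variable", followed by "Any difference with a $p < 0.05$ will be considered statistically significant". No variable, pair of groups or pair of time points is attached to the rule, and no paired or repeated-measures method is listed.

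Section 4 (Phase 1) describes a single group: "patients are enrolled, with the characteristics indicated below, in a number equal to 50". No control arm or subgroup is defined anywhere. The follow-up agenda in section 4 then measures the same patients at enrolment and at monthly, quarterly, six-monthly and annual checks. Section 7 puts entry values and follow-up results on one form per patient.

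The only comparison that section 8 names is the cost of the traditional path against the cost of the model. No test is assigned to it, and this point makes no claim about it.

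**The concern.** All three listed tests assume that the two sets of values come from different patients. In a one-cohort study without declared subgroups, an obvious candidate for a tested difference is enrolment against a later value in the same people. Section 9 also expects the model to improve care, and with no comparator cohort such improvement would naturally be sought as change from enrolment. For that contrast the list contains no suitable test.

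Two things are at stake. First, whatever contrast is meant, a reader of the results cannot tell which of many possible comparisons a p-value below 0.05 was chosen from. Second, if the rule is applied to change and values in the same patient are positively correlated, the tests are too conservative, and a real change in a secondary measure could be reported as not significant.

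**Working it through.** **Inputs from the documents.** n = 50 (sections 4 and 8); significance level 0.05 (section 8). Section 8 gives no power, effect size, SD, rate or dropout for the 50, so there is no calculation of the plan's own to reproduce.

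**Assumed, because the documents give nothing.** Two-sided testing; within-patient correlation ρ of 0.3, 0.5, 0.7 (continuous) or φ of 0.1, 0.3, 0.5 (binary); a change of 0.4 SD, or 60% to 80%, or 70% to 85%; 50, 40 or 20 complete pairs.

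**1. Continuous measure.** With unit SD, the mean change has variance 2(1−ρ)/n, but the unpaired t-test works with about 2/n. Its statistic therefore has a null SD of about √(1−ρ), and its large-sample true size is 2[1 − Φ(1.96/√(1−ρ))]:

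- ρ = 0.3: 1.96/0.837 = 2.34, size 1.9%
- ρ = 0.5: 1.96/0.707 = 2.77, size 0.6%
- ρ = 0.7: 1.96/0.548 = 3.58, size 0.03%

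Simulating the unpaired t-test itself (4,000,000 draws) gives the sizes in the table. Paired power uses the noncentral t with n−1 df and noncentrality 0.4√n/√(2(1−ρ)). For n = 50 this is 2.828/√1.4 = 2.39, 2.828/1 = 2.83 and 2.828/√0.6 = 3.65, against a critical value of 2.01.

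| Pairs | Quantity | ρ = 0.3 | ρ = 0.5 | ρ = 0.7 |
|---|---|---|---|---|
| 50 | True size, unpaired t | 2.0% | 0.6% | 0.06% |
| 50 | Power, unpaired t | 51% | 51% | 52% |
| 50 | Power, paired t | 65% | 79% | 95% |
| 40 | Power, unpaired t | 41% | 40% | 37% |
| 40 | Power, paired t | 55% | 69% | 89% |

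At ρ = 0 and 50 pairs the two tests are nearly equal (51% unpaired, 50% paired). At ρ = −0.3 the unpaired test errs the other way, with a true size of 8.5%.

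**2. Binary measure.** The share positive at both times is p11 = p1·p2 + φ√(p1·q1·p2·q2), with q = 1−p. For 60% to 80% at φ = 0.3: 0.48 + 0.3 × √(0.24 × 0.16) = 0.539, so the discordant shares are 0.6 − 0.539 = 0.061 and 0.8 − 0.539 = 0.261. Summing the four-cell multinomial exactly, with uncorrected chi-square on the two margins as if they were independent groups:

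| Pairs | Setting and test | φ = 0.1 | φ = 0.3 | φ = 0.5 |
|---|---|---|---|---|
| 50 | 60% both times, chi-square size | 4.1% | 2.1% | 0.6% |
| 50 | 60% to 80%, chi-square power | 60% | 61% | 63% |
| 50 | 60% to 80%, exact McNemar power | 55% | 66% | 82% |
| 50 | 60% to 80%, mid-p McNemar power | 62% | 74% | 88% |
| 50 | 70% to 85%, chi-square power | 44% | 43% | 41% |
| 50 | 70% to 85%, exact McNemar power | 38% | 46% | 60% |
| 40 | 60% to 80%, chi-square power | 50% | 50% | 49% |
| 40 | 60% to 80%, mid-p McNemar power | 52% | 62% | 79% |
| 20 | 60% to 80%, chi-square power | 28% | 25% | 21% |
| 20 | 60% to 80%, exact McNemar power | 17% | 19% | 20% |
| 20 | 60% to 80%, mid-p McNemar power | 26% | 30% | 35% |

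Exact McNemar has less power than chi-square at φ = 0.1, and at 20 pairs for all three correlations. Mid-p McNemar matches or beats chi-square except at 20 pairs with φ = 0.1.

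**3. Measures with both values for every patient.** In the section 4 agenda, an enrolment value and an unconditional later one exist for blood pressure and heart rate (monthly), 12-lead ECG (six-monthly and annual) and blood chemistry (annual; the quarterly and six-monthly tests depend on age or renal function). Drug therapy is listed only at enrolment, with the note "evaluated at each therapeutic insertion".

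**The case against.** The strongest reply is that no misuse is documented. The analysis is declared descriptive, the rule refers only to differences, and naming an unpaired t-test reads most naturally as a comparison between patients, for example by age or renal function, where the listed tests are valid. This stands in part. A reader might infer that the plan will test before-after change with the wrong tests, but the documents do not say so, and the power loss is therefore conditional. The reply does not remove the gap, because no between-patient contrast is declared either.

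A second reply concerns endpoints. A reader might take two secondary objectives, "assessment of the prescriptive appropriateness of the dosages and molecules used" and "assessment of the occurrence of pharmacological problems related to drug-drug interactions", as the affected before-after measures. The documents do not support this. Neither has a scheduled second value: therapy review is tied to new insertions, and no timetable is given for the interaction check. Using only patients with two values could select those whose therapy changed, in unknown number.

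A third reply is that paired tests do not always gain power. This is correct for exact McNemar at low correlation or with few pairs, which is why mid-p McNemar is proposed.

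Finally, the continuous figures illustrate scheduled measurements such as blood pressure, which no stated objective names. That also stands, and it limits the weight of the point.

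**Conclusion.** The point holds in a limited form and should be fixed. It is certain that section 8 sets a significance rule, lists only independent-group tests and names no contrast, in a study of one cohort measured repeatedly. It is conditional that power is lost: this requires that the rule be applied to change in the same patients and that their values be positively correlated. Under the assumed correlations and 50 pairs, power for a 0.4 SD change is about 51% instead of 65% to 95%. For a binary change from 60% to 80% it is 60% to 63% by chi-square against 62% to 88% by mid-p McNemar. The difference is negligible at low correlation, and can reverse with few pairs.

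A reader might also infer that false-positive findings are likely or that the main result is unsound. Neither follows. Ignoring positive correlation makes the tests conservative; inflation would need negative correlation, for which the documents give no reason. The descriptive primary objective, outcomes that arise only during follow-up (such as bleeding events or acceptance of reports) and the anonymous end-of-study questionnaire are unaffected.

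**What to change.** In section 8, list each contrast to be tested, with its variable and time points. For change, restrict the list to measures with an enrolment value and a scheduled later value for all patients: blood pressure and heart rate, 12-lead ECG, and blood chemistry at the annual check. Then replace the sentence on tests with wording such as:

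> Change in the same patients will be tested by paired t-test or Wilcoxon signed-rank test (continuous) or mid-p McNemar test (binary), in patients with both values; the number of pairs will be reported. Chi-square, unpaired t-test and Mann-Whitney U will be used only for the named contrasts between different patients, with one value each.

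Test change in prescriptive appropriateness or drug interactions only if the therapy records allow an end-of-study classification for every patient, not just for those whose therapy changed. Otherwise describe these outcomes.

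If no test is intended, delete the two testing sentences and report estimates with 95% confidence intervals.

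The cost is a few sentences in section 8 and slightly more analysis work. The scheduled measures need no new visits or patients.
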